#### 9 DESCRIPTION OF STUDY VISITS

Each participant will have a 42-day screening period followed by 12 weeks of treatment at home. The study visits are described below and outlined in the Schedule of Events in Appendix 1.

Ver. 3.1; 09-25-2023

## 9.1 Screening Visit

The screening visit should occur up to 42 days before the baseline visit. The screening visit procedures may be completed over multiple days, but all must be done within a week. At PI's discretion, re-testing can be done within 30 days. If the investigator deems re-screening is justified, they must contact Medical Monitor and sponsor for discussion on a case-by-case basis. If/when rescreening MMSE, the test has to be done at least 3 weeks apart from the previous one.

Potential participants or their legally authorized representatives (LAR) if PI deems that participant cannot fully understand ICF to give consent, must sign an informed consent form prior to administration of any study-related procedures. The informed consent process must be performed by the principal investigator or medically qualified sub-investigator. Information regarding the participant's demographics, concurrent medications, and medical history will be collected along with cognitive assessments, physical examination, and neurological examination.

Safety assessments will include an ECG that will need to be read locally and reviewed by the site investigator to confirm eligibility. The clinical safety laboratory blood and urine tests will be sent to a central lab for analysis. The screening safety laboratory tests will be comprised of a metabolic panel, complete blood count, and urinalysis as listed in Section 12.1.3. Urine dipstick pregnancy test will be completed for female participants of childbearing potential. Fasting is required for safety laboratory tests.

Cognitive and functional assessments should not be administered when the participant is in a fasted state. Once all screening visit procedures are completed, all information related to eligibility, including screening lab results, must be reviewed by the site investigator to assess the participant's eligibility before proceeding to Baseline.

#### 9.2 Baseline Visit

Sites should remind participants 1-3 days prior to their onsite visit through a telephone call. Baseline procedures include functional, cognitive, and behavioral assessments, safety assessments and a review of concurrent medications and potential adverse events that might occur. To avoid the learning effect, MMSE should be done at least three weeks after the participant's last MMSE test. The visit will consist of the following: admission procedures, including genetic material collection (blood for ApoE genotype), PK Sampling / administration of first dose, and finally, discharge procedures.

Fasting state is required for safety laboratory tests, however, cognitive, and functional assessments should not be administered when the participant is in a fasted state.

All baseline assessments should be performed on the same day. Details as below.

Confidential Page 40 of 57

Participants should arrive fasted in the morning after an overnight fast. Clinical safety labs will be drawn and sent to the central lab for analysis.

After safety lab, participants will be provided low-fat light meal before completing functional and cognitive evaluations, a physical and neurological exam, collecting vital signs, ECG, and reviewing and recording adverse events and concurrent medications. Sites should take detailed notes of the contents of all meals provided to the participants. Following completion of all these procedures, participants who continue to meet all protocol inclusion criteria and no exclusion criteria should be randomized.

If no medical or compliance concerns are identified, the participant will move on to the PK sampling phase, which will entail the following procedures:

- 1) Collect initial samples of blood (hour 0) (12ml) with venipuncture unless PI deems inappropriate with 2ml in a tube for ApoE genotype\* and 10ml in a separate tube for PK.
- 2) Administer first dose of assigned study drug after the hour 0 sampling.
- 3) Collect blood (10mL) at the 1hr, 2hrs and 4hrs timepoints. Blood should be taken within ± 10 mins of times.
- 4) Perform the final safety monitoring.

Prior to discharge from the clinic, vital signs should be recorded, and a review of AE(s) and concomitant medications should be conducted. Participants will be educated of the study drug compliance and study drug return. Upon determination by the Investigator (or qualified designee) that the participant is stable, the participant will be discharged. If a participant experiences an unstable AE, please contact the Medical Monitor for guidance on the appropriate course of action to be taken.

#### 9.3 Onsite Visit at 6 Weeks

Sites should remind participants 1-3 days prior to their onsite visit through a telephone call. At 6 weeks from the baseline visit, a clinic visit should occur. Clinic visit procedures include functional, and cognitive assessments, safety assessments, and review of concurrent medications and adverse events. Fasting is required for safety laboratory tests.

After safety lab, participants will be provided low-fat light meal before completing functional and cognitive evaluations, a physical and neurological exam, collecting vital signs, ECG, and reviewing and recording adverse events and concurrent medications. Sites should take detailed notes of the contents of all meals provided to the participants.

Confidential Page 41 of 57

\* ApoE genotype sample can be collected along with any other blood draw during this visit, as deemed appropriate by PI.

Study medication compliance will be reviewed and discussed, and reminders given about the upcoming end of trial visit. The participant should be scheduled for the 12-week clinic visit.

#### 9.4 12 Weeks Visit (End of Trial Visit)

Sites should remind participants 1-3 days prior to their onsite visit through a telephone call. Admission for the end of trial visit should occur 12 weeks following the first dose of study medication. A pre-visit phone call will be conducted 1-3 days prior to admission and a post-visit phone follow-up will be conducted approximately 24 hours following discharge. End of trial visit procedures include functional, and cognitive assessments, safety assessments, and review of concurrent medications and adverse events that occur in clinic and blood collection. Fasting state is required for safety laboratory tests, however, cognitive, and functional assessments should not be administered when the participant is in a fasted state.

#### 9.4.1 End of Trial Visit

This constitutes the participants' last clinical visit during the study. The end of trial visit will consist of the following: admission procedures, blood sampling, all psychometric and safety tests, and discharge procedures. Fasting is required for safety laboratory tests.

Participants should arrive fasted in the morning after an overnight fast. Clinical safety labs will be drawn and sent to the central lab for analysis.

After safety lab, participants will be provided a low-fat light meal before completing functional and cognitive evaluations, a physical and neurological exam, collecting vital signs, ECG, and reviewing and recording adverse events and concurrent medications. Sites should take detailed notes of the contents of all meals provided to the participants.

If no medical or compliance concerns are identified, the participant will move on to the PK sampling phase, which will entail the following procedures:

- 1) Collect initial samples of blood 10ml (hour 0) with venipuncture unless PI deems inappropriate.
- 2) Administer last dose of assigned study drug after the hour 0 sampling.
- 3) Collect blood (10mL) at the 1hr, 2hrs and 4hrs timepoints. Blood should be taken within  $\pm$  10 mins of times.
- 4) Perform the final safety monitoring.

Prior to discharge from the clinic, vital signs should be recorded, and a review of AE(s) and concomitant medications should be conducted. Upon determination by the Investigator (or qualified designee) that the participant is stable, the participant will be discharged. If a participant experiences an unstable AE, please contact the Medical Monitor for guidance on the appropriate course of action to be taken.

Confidential Page 42 of 57

## 9.4.2 Post End of Trial Visit 24-Hour Phone Follow-up

Approximately 24 hours following the end of trial visit the participant will be contacted by phone to confirm the participant's well-being and to query about any new AEs.

Ver. 3.1; 09-25-2023

Confidential Page 43 of 57

#### 10 EARLY TREATMENT/STUDY DISCONTINUATION

The investigators at each site will make every reasonable effort to maximize participant retention. However, if an investigator removes a participant from treatment or study, or if a participant declines further treatment or study participation, an early discontinuation visit will be completed as soon as possible following discontinuation.

Ver. 3.1; 09-25-2023

Participants who discontinue from the study prior to completing all protocol procedures may be replaced in consultation with the Sponsor.

## 10.1 Reasons for Early Discontinuation

Participants or their LARs may withdraw from the study at any time as stated in the informed consent document given to the participant at the time of enrollment. Participants or their LARs should inform sites as soon as such a withdraw decision is made. Participants must also be discontinued from treatment/study for reasons such as the following:

- Adverse experience: The participant has experienced an adverse event that, in the opinion
  of the investigator, requires early discontinuation. This may include abnormal laboratory
  values.
- Death.
- Safety risk: Any participant who becomes a safety risk to themselves during the trial will be withdrawn.
- Protocol violation: The participant fails to meet protocol entry criteria during the study after being randomized or does not adhere to protocol requirements. \*
- Development of suicidal or homicidal ideation requiring hospitalization or confinement.
- Consent is withdrawn. The participants or their LARs wishes to withdraw from the study.
- The study is terminated by the Sponsor/Coordinating Center, alone or at the recommendation of the Data Safety Monitoring Board.
- Lost to follow up. Participant could not be recalled back to conduct follow up visits.
- \* The line item above requires the participant to continue to meet study entry criteria after randomization. This means that assessments conducted at visits post-randomization, such as vital signs, ECG, and laboratory tests, with results that fall outside of the parameters outlined in the Inclusion/Exclusion criteria must be discussed with the Medical Monitor and Study Team.

The investigator and Medical Monitor will review the case to determine whether the participant must be discontinued from the study based on the abnormal value or if it is safe for the participant to continue treatment.

Confidential Page 44 of 57

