#### 4.2. Study Overview

**Study population:** The study will be conducted in a diverse population of participants with mild to moderate AD.

**Dose selection**: Qualified participants will be randomly assigned at a 1:1:1:1 ratio to one of the four treatment arms: buntanetap 7.5 mg, buntanetap 15 mg, buntanetap 30mg, and placebo.

**Study Design:** 320 mild to moderate AD participants will be randomized to 7.5 mg, 15 mg, 30mg of buntanetap QD or placebo. If they provide informed consent, they will undergo a Screening Visit, and if they are considered eligible per the inclusion and exclusion criteria, they will proceed to participate in the treatment period. Randomized participants will visit the clinic for the first-time dosing in clinic, followed by an at home dosing period of 12 weeks, with daily administration of 7.5 mg, 15 mg, or 30 mg of buntanetap or placebo. Participants will be required to visit clinics Day 0 (baseline), 6 weeks, and 12 weeks (end-of-trial), where they will

Confidential Page 21 of 57

undergo study procedures that include safety assessments (AE and concomitant medication monitoring, 12-lead ECGs, clinical laboratory testing, vital signs assessments, and physical/neurological examinations) and psychometric tests (ADAS-Cog11, ADCS-CGIC, ADCS-ADL, DSST, MMSE). At the end of blood sampling, the participants will need to stay for a minimum of 1 hour of observation. After all end-of-study procedures are complete, the participant will be discharged to home. A 24-hour follow-up call will occur after all clinical visits to assess the participants current condition and if there are any additional adverse events or questions.

Participants who drop out during the initial 9 weeks at home treatment period will be discontinued and complete an early discontinuation visit as soon as possible following discontinuation. Participants that drop out after the initial 9 weeks will be scheduled for an end of trial visit. If 4 participants are discontinued due to severe adverse events a DSMB safety review will be conducted without interrupting the study.

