# 6.3. Safety and Tolerability Analysis

Safety and tolerability will be assessed with physical examinations, vital signs, clinical laboratory values, 12-lead ECG, use of concomitant medications, and AE reports. The frequencies of adverse events, serious adverse events, and laboratory abnormalities between the participants across the treatment groups will be compared.

Confidential Page 24 of 57

Participants who dropout during the initial 9 weeks at-home treatment period will be discontinued and invited to an Early Discontinuation visit. Participants that drop out after the initial 9 weeks will be scheduled for an end-of-trial visit. If 4 participants are discontinued due to serious adverse events a DSMB safety review will be conducted without interrupting the study.

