# 7.6 Compliance

Site personnel will assess compliance based on the amount of study drug dispensed to and returned by the participants, together with any related information, including the administration of study drug by study staff during the end of trial visit. Participants are encouraged to maintain a minimum of 80% compliance with study drug administration across the 12 weeks at home dosing period.

Prior to the end of trial visit, site personnel will also contact the participant to remind them of the dose regimen, to ensure that a good level of compliance has been achieved.

Confidential Page **33** of **57** 

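### A consenting participant who stops study drug before Week 9 has no planned Week 12 efficacy assessment, because stopping drug and leaving the study share one follow-up path

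*Protocol*

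**What the plan says.** Protocol 10 orders the same action whether a participant is removed from, or declines, treatment or the study: "an early discontinuation visit will be completed as soon as possible following discontinuation". Section 10.1 continues in the same way: "Participants must also be discontinued from treatment/study for reasons such as the following". Section 4.2 sets the timing: "Participants who drop out during the initial 9 weeks at home treatment period will be discontinued and complete an early discontinuation visit". Section 6.3 is softer: "Participants who dropout during the initial 9 weeks at-home treatment period will be discontinued and invited to an Early Discontinuation visit". Schedule footnote b agrees with both. Participants who drop out after 9 weeks get the End-of-Trial visit, so they are outside this point.

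The 10.1 footnote on out-of-range results offers two outcomes, that the participant "must be discontinued from the study based on the abnormal value or if it is safe for the participant to continue treatment". Being off drug but still followed is not among them. Section 10 also lets people who leave early be replaced ("may be replaced in consultation with the Sponsor"). The 10.1 list of reasons includes a participant who "does not adhere to protocol requirements", with no threshold, while 7.6 says only: "Participants are encouraged to maintain a minimum of 80% compliance with study drug administration".

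Other text does keep the two events apart. Protocol 6.7.2 tabulates stopping treatment and withdrawing as separate items. SAP 8.3.1 counts adverse events leading to each separately. Protocol 19 withdraws pregnant participants from treatment only. None of this schedules a later efficacy visit.

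On analysis, SAP 8.2.7 makes ITT the primary set, and SAP 7 analyses it by randomised treatment. SAP 8.2.3 limits the MMRM to Week 6 and Week 12. SAP 8.8 states the missing-at-random assumption, names leaving the study for any reason as the intercurrent event, and adds placebo-based multiple imputation for both co-primary endpoints as a sensitivity analysis.

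**The concern.** Take a participant who stops capsules in Week 3 for an adverse event and is willing to return. Under the written path that person has an early discontinuation visit at about Week 3 and no Week 12 value. Both co-primary scales are collected at that visit, but soon after stopping, and the SAP does not say whether those scores count as Week 6, as Week 12 or not at all. Replacement restores the head count but not that person's outcome.

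The MMRM then infers the Week 12 value mainly from people in the same arm who stayed on drug. If the question is the effect regardless of stopping, which fits an ITT, as-randomised analysis, the inferred value may credit the stopper with benefit that was lost. Imputation can explore that possibility. It cannot replace an outcome that could have been observed at a visit already on the schedule.

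**Working it through.** **Inputs from the documents** (Protocol 6.2, 6.10.1; SAP 6): 3:1 pooled active to placebo; ADAS-Cog11 difference 2.7, SD 6.0; ADCS-CGIC difference 0.23 (0.22 in 6.10.1), SD 0.5; two-sided 0.05; 280 evaluable; 12.5% dropout; 320 randomised.

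**The plan's own figure.** With 210 v 70, noncentral t power is 90.1% for ADAS-Cog11, and 280/(1 − 0.125) = 320. Both reproduce.

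**Assumptions** (the documents give no dropout timing, reasons or willingness to return): dropout is even over 12 weeks and over arms; early discontinuation scores are not used as Week 12; End-of-Trial visits after Week 9 count as Week 12; the target is the effect regardless of stopping; and missing at random credits a stopper with the full on-drug effect. The last is a simplification, since those stopping in Weeks 6 to 9 contribute a Week 6 value.

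**Participants affected.** Dropouts: 0.125 × 320 = 40. Before Week 6: 40 × 6/12 = 20. Weeks 6 to 9: 40 × 3/12 = 10. Total before Week 9: 30. If 50% to 90% of stopping falls before Week 9, the total is 20 to 36.

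**Bias removed** = (number followed/320) × difference × (1 − share of effect kept):

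| Followed to Week 12 | ADAS-Cog11, none kept | ADAS-Cog11, half kept |
|---|---|---|
| 7.5 (a quarter of 30) | 0.06 | 0.03 |
| 15 (half of 30) | 0.13 | 0.06 |
| 30 (all, ceiling) | 0.25 | 0.13 |

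For example, 15/320 × 2.7 = 0.127. With half followed and the affected total at 20 or 36, the none-kept figure is 0.08 (10/320 × 2.7) or 0.15 (18/320 × 2.7). For ADCS-CGIC, 15/320 × 0.23 = 0.011, or 0.005 if half is kept.

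**Against the standard error.** SE = 6 × √(1/(0.75N) + 1/(0.25N)). The current path gives N = 290 (280 plus the 10 who stop after Week 9) and SE 0.814, so 0.127/0.814 = 0.16 SE. With 15 more, N = 305 and SE is 0.793, a fall of 2.5%. The fall is 1.9% to 2.3% once Week 6 values inform the model, at an assumed visit correlation of 0.8 to 0.5.

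**If adopted after the interim.** SAP 8.9 says the re-estimation, set for 90 participants with Week 6 data, has been done. Scaling to the rest gives 30 × (320 − 90)/320 = 21.6, so at most about 22 people. If half return, 11/320 × 2.7 = 0.09 points. The number shrinks as enrolment proceeds.

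**Power** (noncentral t, 3:1, true on-drug difference 2.7):

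| Scenario | Stoppers keep none | Stoppers keep half |
|---|---|---|
| Current path: 290 assessed, 10 stoppers | 2.7 × (1 − 10/290) = 2.607; 89.1% | 90.2% |
| Half of 30 followed: 305 assessed, 25 stoppers | 2.7 × (1 − 25/305) = 2.479; 87.6% | 90.2% |
| All followed: 320 assessed, 40 stoppers | 2.7 × (1 − 40/320) = 2.3625; 86.0% | 90.3% |

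For ADCS-CGIC with none kept, the first two rows give 90.4% and 88.9% at a difference of 0.23, or 87.7% and 86.1% at 0.22.

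**The case against.** The strongest reply is that SAP 8.8 already covers the feared case. Imputing non-completers from placebo is close to assuming that stoppers keep none of the effect, and it is prespecified for both co-primary endpoints. That stands and is the main reason the gap is limited. What remains is that some of those values could be observed instead.

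The second reply is that the bias depends on the target. If the target is the effect had participants continued, missing at random is consistent with it. The SAP names an intercurrent event but no strategy, so a reader might infer that the primary estimate is biased. The documents do not settle that. Collecting the data serves either target, since off-drug values can be set aside later.

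Third, a reader might infer that the plan treats stopping drug and leaving the study as one event throughout. It does not: disposition and adverse event reporting separate them. Only the follow-up path is shared. Sections 4.2 and 6.3 and footnote b speak of dropping out, which could mean leaving the study; Sections 10 and 10.1 are what join the two. Section 10 also asks sites to make every reasonable effort at retention, though it sets no off-drug visit.

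Fourth, a reader might infer that participants are removed for missed doses. The text permits this but does not show it: the 10.1 footnote explains that item through entry criteria and Medical Monitor review, 7.2 and 7.6 only encourage compliance, and 7.8.1 refers prohibited drug use to the Medical Monitor.

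Finally, the share who would return has no source. Death, withdrawn consent and loss to follow-up are in the 10.1 list and are not recoverable. That is why a range is given.

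**Conclusion.** The point holds in limited form. The follow-up path leaves a consenting participant who stops drug before Week 9 without a planned Week 12 efficacy assessment, and the SAP does not place the early discontinuation scores in its model. The existing sensitivity analysis contains the risk but does not supply the data.

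On the stated assumptions, a rule in force from the start would remove about 0.06 to 0.13 ADAS-Cog11 points if a quarter to a half of about 30 early stoppers return and keep none of the effect, with a ceiling of 0.25. All three figures halve if they keep half. It would be wrong to count all 30 as recoverable by an amendment made now: after the interim the figure is at most about 22 people, or about 0.09 points if half return. This is an inexpensive improvement worth making. It is not grounds to doubt the primary analysis.

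**What to change.** In Protocol 4.2, 6.3, 10 and 10.1 and schedule footnote b, separate stopping study drug from withdrawing from the study. Then:

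- keep the prompt early discontinuation visit for everyone who stops, for safety;
- ask participants who stop drug but still consent to attend whichever of the scheduled Week 6 and Week 12 efficacy visits remain;
- record the drug-stop date;
- state that non-adherence alone is not a reason to leave the study;
- in the SAP, include the off-drug Week 6 and Week 12 values as observed in the ITT MMRM, say how early discontinuation scores are handled, and keep the SAP 8.8 imputation for values still missing.

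Who stops drug, and why, does not change.

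The cost is amendment wording and one or two already scheduled visits for at most about 30 participants, some of whom will decline. If half of the 30 return and stoppers keep no effect, ADAS-Cog11 power is 87.6% instead of 89.1%; if they keep half, it is unchanged. The lower figure reflects a smaller true effect regardless of stopping. No sample size increase is proposed. The 100-per-arm maximum is not available as an offset, because it applies only under the interim conditional-power rule, which has already been run.
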